5.2 Secondary Estimands

The first of the two secondary estimands is the difference in mean gene expression from non-lesional skin tape transcriptome at Day 7, and separately at Day 168-224, between Non-AD vs. Mild DNAD and Non-AD vs. Moderate-to-severe DNAD children (6-17 years old), and separately adults (18+ year olds), enrolled in this study.

The second of the two secondary estimands is the mean change in normalized gene expression between Day 7 and Day 168-224 non-lesional skin tape transcriptomes, among topical steroid responders, dupilumab responders, dupilumab non-responders, non-AD, and long-term dupilumab responders in children (6-17 years old), and separately in adults (18+ year olds) enrolled in this study.

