8.2 Stratification and covariates

Throughout analysis, our approach will be to analyze pediatric and adult populations separately to better model and discover any cohort-specific endotypes and phenotypes. We will then compare how effects of interest differ between the two age cohorts. We will also fit combined pediatric/adult models using interaction terms with age group to help identify effects that are shared and unique to age groups. In regards to skin sampling, in addition to skin tape strip (STS) samples collected from all children and adults at each sample point, we will be collecting required and optional biopsy samples from adults, depending on time point and course of treatment. We may in certain instances compare biopsy and STS samples, as information from these samples can be complementary. For AD participants, skin samples will be collected from both lesional and non-lesional skin, as applicable. Although main analyses will focus on non-lesional skin, such that signatures of AD disease and severity can specifically be tied to systemic effects on skin tissue rather than to the unique character of lesional skin, we will also investigate how AD and treatment effects differ between the two skin types.

Finally, as transcriptional responses to AD or AD treatments can also be influenced by individual traits, such as age, sex, race/ethnicity, body mass index (BMI), concomitant therapies, concomitant asthma, age of asthma diagnosis, asthma controller usage, presence and frequency of eczema herpeticum, history of Staph infection, presence of recurrent or chronic sinusitis, modified rhinitis symptom utility index (MRSUI) total score, presence and type of food and animal allergies, presence and treatment of viral/bacterial infections, smoking status and pack years of the participant or caregiver, level of compliance for the different treatments, and existence and type of adverse events, we may include these as covariates in the models below where appropriate, to ensure that such variables don't confound our inferences. Where significant, effects of these covariates on responses will be investigated by running sensitivity analyses on datasets stratified based on these covariates.

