To investigate changes in skin gene expression due to standard-of-care treatment as delineated in the protocol and how these changes may differ with study outcome groups (i.e., groups based on treatment regimen and response), we will model gene expression at both Day 7 and End of Study (Day 168-224) Visits using linear mixed models. Gene expression data will be normalized using the VST method. Models will include fixed effect variables for visit, study outcome group (topical steroid responders, dupilumab-naïve responders, dupilumab-naïve non-responders, non-AD, and long-term dupilumab participants), and visit x

study outcome group interaction, along with relevant covariates and a random intercept for each participant to account for pairing of Day 7 and End of Study samples. Among the covariates, there will be a binary variable that further distinguishes topical steroid responders who had mild AD to begin with since baseline (set covariate = 1) versus those who actually improved from having moderate-to-severe AD at baseline (set covariate = 0) in order to consider them as “true” topical steroid responders to compare with among the other outcome groups in the model (all remaining groups would set covariate = 0 as well). Using this model, we will examine responses to standard-of-care treatment as delineated in the protocol by contrasting Day 7 and End of Study Assessment Visits within outcome groups. We will also examine differences in response to standard-of-care treatment between any two outcome groups by testing the interaction term for visit effect in one outcome group versus another.

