The 34 models defined above will then be repeated with additional covariates as described in Section 8.2. If a covariate is found to be statistically significant in the model and if deemed appropriate, we will carry out sensitivity analyses by repeating analysis in participants stratified into covariate-based groups to determine whether effects qualitatively differ among stratified groups. For continuous covariates, this will require discretization. If sufficient samples are available for covariate-based groups, we may also fit a single model that includes the covariate and disease group with covariate interaction terms, enabling us to quantitatively determine whether disease effects differ by the covariate.

Pathway and enrichment analyses will be performed on DEG sets.

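### SAP 9.2.2 names no visit × covariate term for SO2 apart from age group, so adjusting for person-constant covariates leaves the Day 7 to End of Study contrasts essentially unadjusted

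*SAP*

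**What the plan says.** - **Target.** SAP 5.2: "The second of the two secondary estimands is the mean change in normalized gene expression between Day 7 and Day 168-224", for each outcome group, in children and adults separately.
- **Model.** SAP 9.2.2: "Models will include fixed effect variables for visit, study outcome group" and their interaction, "along with relevant covariates and a random intercept for each participant to account for pairing of Day 7 and End of Study samples". Models 1 and 12 carry the estimand. The pairwise group comparisons (Models 2–11 and 13–22) are supportive.
- **The one covariate spelled out.** "there will be a binary variable that further distinguishes topical steroid responders who had mild AD to begin with since baseline". It is fixed per participant and also has no visit interaction.
- **Adjusted repeats.** SAP 9.2.2: "The 34 models defined above will then be repeated with additional covariates as described in Section 8.2". Section 8.2 lists 17 items and gives the purpose: "we may include these as covariates in the models below where appropriate, to ensure that such variables don't confound our inferences".
- **Follow-up.** If a covariate is significant, and if it is thought appropriate, the analysis is rerun within covariate strata to see whether effects differ qualitatively. The team may also fit "a single model that includes the covariate and disease group with covariate interaction terms".
- **Age group.** Adults and children are modelled separately. Combined models with age-group interactions are also planned (SAP 8.2 and 9.2.2, Models 31–34).

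**The concern.** Where the SAP wants an interaction it says so: visit × outcome group, skin type × visit, age group. For the other covariates it says only that they are included or added, so main effects are the natural reading. A main effect of something that does not change between two visits shifts both visits equally. It cannot alter the difference between them, and that difference is what SO2 estimates.

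The outcome groups are formed by treatment course and EASI response (SAP 6.2), not by randomisation. Comparisons of change between groups therefore need protection from confounding. If the repeats return almost the same contrasts by construction, their agreement would be read as robustness when it is largely an algebraic result.

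**Working it through.** **1. The plan's own figures.** Adult group sizes follow from Protocol 13.7.1: steroid non-responders 160 × 0.50 + 100 × 0.05 = 85; steroid responders 260 − 85 = 175; dupilumab responders 0.40 × 85 = 34; dupilumab non-responders 51; with 100 non-AD and 40 long-term dupilumab. Table 13.7.1.3 follows from FC = exp{√[2(z₁₋α/₂ + z₀.₈)²(1/depth + CV²)/n]}, with α = 0.05/10,000 (two-sided assumed), depth 10 and CV 0.4. For n = 175: 2 × (4.565 + 0.842)² × 0.26/175 = 0.0869, and exp(√0.0869) = 1.34, as printed. All 20 entries reproduce. The table involves no covariates and is unaffected.

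**2. Algebra.** For participant *i* in group *g*, y(visit) = intercept + group + γxᵢ + uᵢ + visit × (β + δ_g) + error. The within-person difference is β + δ_g + (difference of errors). Both γxᵢ and uᵢ drop out. With complete pairs, the visit and visit × group contrasts depend only on these differences, so adding xᵢ cannot move them. An outcome group × xᵢ term without visit drops out in the same way.

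**3. Numerical check, complete pairs.** REML random-intercept fits on one simulated adult data set (175/34/51/100/40). Effects and variances are assumed: a covariate averaging 0.8 units higher in both dupilumab groups raises the change by 0.3 per unit. The built-in covariate-adjusted difference in change, dupilumab non-responders minus non-AD, is −0.1. Change (SE):

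| Model | Steroid responders | Dupilumab non-responders | Non-AD |
|---|---|---|---|
| Unadjusted | −0.46297 (0.05933) | 0.21228 (0.10990) | −0.00749 (0.07849) |
| + person-level main effects | identical | identical | identical |
| + group × covariate, no visit | identical | identical | identical |
| + visit × covariate | −0.61956 (0.08723) | −0.02939 (0.11265) | 0.03521 (0.08064) |

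The other two groups behave the same way. The last row is read at covariate value zero, so the between-group difference is the useful comparison. Dupilumab non-responders minus non-AD is 0.21228 + 0.00749 = 0.220 unadjusted and with main effects. With visit × covariate terms it is −0.02939 − 0.03521 = −0.065.

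**4. With 20% of End of Study samples missing.** The results are no longer identical. Over 30 simulated data sets the mean absolute shift from main-effect adjustment was 0.16 SE and the largest 0.63 SE. In one such set the same difference was 0.20138 + 0.00257 = 0.204 unadjusted, 0.19573 + 0.02132 = 0.217 with main effects, and −0.01506 − 0.01650 = −0.032 with visit × covariate terms.

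**5. What does move the change.** A covariate that varies between visits, entered as a main effect, moved the steroid-responder change from −0.463 to −0.224. Refitting within covariate strata gave −0.63 and −0.24.

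**6. The stratification trigger.** A significant main effect tests average expression over both visits, not change. In a separate simulation (400 adults, change shifted by 0.3–0.8 SD), a covariate acting in opposite directions at the two visits met the trigger about 5% of the time. One acting only at End of Study met it from 39% to over 99% of the time.

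**7. The interaction sentence.** The same words close SAP 9.1.1, where disease group is the response of a single-visit model. The SO2 models contain visit and outcome group. A disease group × covariate term without visit describes differences in level, not in response to treatment.

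**8. Illustration of the stakes.** Assume a binary covariate present in 60% of one group (n = 51) and 15% of the other (n = 100) that shifts the change by 0.5 SD. The bias is (0.60 − 0.15) × 0.5 = 0.225 SD, against a standard error of √(1/51 + 1/100) = 0.172. Simulated per-gene false-positive rates at a nominal 5% were about 13%, 26% and 50% for shifts of 0.3, 0.5 and 0.8 SD, and about 5% with a visit × covariate term.

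**The case against.** Several points on the other side stand and limit the conclusion.

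- **Stratified reruns.** They refit visit and visit × group at each covariate level, so they do re-estimate the change. A reader might infer that the plan has no working protection against confounding; the SAP does not support that. The reruns remain discretionary and qualitative, depend on the trigger in step 6, and give no single adjusted between-group contrast. The groups to be split include 34 adult and 17 child dupilumab responders.
- **Covariates that vary by visit.** Concomitant therapies, MRSUI score, infections, compliance and adverse events can differ between visits and do adjust the change if entered by visit. It would be wrong to say that no Section 8.2 covariate reaches the change.
- **Age group** is already handled by separate fits and interaction models.
- **The estimand.** SAP 5.2 asks for each group's own mean change. A constant covariate does not confound that, so the concern is with between-group differences, which are supportive.
- **Main effects only** is inferred, not stated. The disease group model is optional and looks like carried-over wording. Severity is defined at the analysis timepoint (SAP 6.2), so disease group could be read as varying by visit, but the sentence still names no visit × outcome group × covariate term.
- **Size.** The confounder in step 8 is assumed, and the 5% per-gene test precedes the Benjamini-Hochberg control in SAP 9.2.1. By normal approximation, at the protocol's power threshold of 0.05/10,000 the same scenarios give roughly 0.01%, 0.05% and 0.5%.

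**Conclusion.** The point holds in this limited form. For covariates constant within a person, the adjusted SO2 repeats return the unadjusted visit and visit × outcome group contrasts exactly with complete pairs. With about 20% of End of Study samples missing they come close (mean shift about 0.16 SE, largest 0.63 SE). Agreement between the two is not evidence that differences in change are unconfounded, so for these covariates the repeats do not serve the purpose given in Section 8.2. The optional interaction model cannot show whether treatment response differs by a covariate.

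This rests on the main-effects reading. The exact result is algebra and needs no assumed values; the dropout figures depend on the assumed simulation. A reader might take the 13–50% rates as the expected error of the analysis. They are not: they illustrate one assumed confounder before false discovery control. The within-group estimand and the power table are unaffected. A change to the SAP is warranted, at the level of a secondary objective.

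**What to change.** In SAP 9.2.2:

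1. Keep Models 1 and 12 without visit × covariate terms as the within-group change of SAP 5.2.
2. In the adjusted repeats, enter a short pre-chosen list of key person-level covariates, mean-centred, each with its visit × covariate term. Read between-group differences in change from that model, and state that its within-group changes are covariate-standardised and so differ from the estimand in SAP 5.2.
3. State which Section 8.2 covariates are entered by visit.
4. Trigger the stratified reruns on the visit × covariate term instead of the main effect.
5. Replace the disease group × covariate sentence by visit × covariate for within-group response and, where numbers allow, visit × outcome group × covariate for between-group differences.

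The cost is SAP wording, lost degrees of freedom and wider intervals. The loss would be notable in the pediatric dupilumab responder, dupilumab non-responder and long-term groups (17, 26 and 20 planned, before dropout). Giving all 17 listed items a visit interaction would be too many there, hence the short list.

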9.3 Analysis of Exploratory Endpoints/Outcomes

Please refer to the Exploratory SAP.

10 SAFETY EVALUATION

Safety data are collected, graded, recorded, and reported according to section 12 of the study protocol. The DAIT/NIAID medical monitor receives, reviews, and makes decisions on monthly reports from the Rho statistical team compiling new and accumulating information on AEs, SAEs, and pregnancies recorded by the study site(s) on appropriate eCRFs. The NIAD Allergy and Asthma DSMB annually reviews safety data

that include, at a minimum, a listing of all reported AEs and SAEs. No further safety evaluation has been planned for the interim or final analyses.

11 PHARMACOKINETIC EVALUATION

None

12 OTHER ANALYSES

None

13 INTERIM ANALYSES AND DATA MONITORING

13.1 Quality Control of RNA-seq Data

Beginning with the first batch of RNA-seq data, we will generate metrics of sample quality, including percent of transcripts mapped (to the genome, to genes, to the mitochondrial genome, etc.), and number of expressed read counts and detected genes per sample. Samples with poor or outlier values for these metrics will be removed or re-sequenced. For AD and non-AD groups, we will examine the most highly expressed genes, most variant genes, enriched pathways thereof (using Enrichr), and identified co-expression networks (using WGCNA) to determine whether expected genes and pathways are expressed within the skin tape and skin biopsy data. Furthermore, once we have at least 10 samples per comparison group, and with every new batch of sequence data thereafter, we will use differential expression analysis to test for gene expression differences based on disease status (AD vs. Non-AD) and severity (AD mild vs. AD moderate-to-severe), to ensure the expected gene expression patterns are observed.

13.2 [REDACTED]

13.2 Interim Analysis of Safety Data

No formal interim analyses are planned for safety.

13.3 Futility Analysis

No formal interim analyses are planned for futility.

14 CHANGES TO THE ANALYSES PLANNED IN THE PROTOCOL

If WGCNA does not capture well type 2 inflammatory gene sets, we may instead use pre-existing type 2 gene sets to define the type 2-high endotype used in carrying out the primary objective. If local EASI and TAA do not well capture local AD severity, we may either modify these measures or use different local severity measures that better capture variation in local AD severity in our population.

